4.4 Surgery and Post-surgical follow-up period

The ECOG performance status, vital signs, body weight, ECG, gleason score, RP, assessment after radical prostatectomy plus ePLND, adverse event, tumor tissue HRRm test will be collected on V5 (EOT+30days). The tumor tissue for HRRm testing will be sent out to central lab within RP+30days.

Radical prostatectomy should be performed for eligible subjects within 30 days after Day 169 /the end of treatment visit. The reason for failure to receive an operation will be collected for the patients without radical operation and a safety follow-up visit will be performed (12 weeks after the last dose of zoladex)

The tumor tissue for HRRm testing will be collected and sent out to central lab within 30 days after RP. All subjects receiving radical operation following NHT will be subject to evaluation of surgery related parameters as well as tumor tissue HRR mutation test after the operation. If scheduled study assessments cannot be obtained because of a holiday, these assessments should be obtained at the soonest following date, unless the soonest following date is not more than 2 days away from the evaluation time of other planned studies.

Descriptions of the procedures for this period are included in the Study Plan with exceptions of the following specific requirements for the follow-up period:

All visits must occur within \pm 5 days from the scheduled date starting at visit 5, unless otherwise noted. All assessments will be performed on the day of the specified visit unless a time window is specified.

ECOG performance status will be performed during post-surgical follow-up period, or at the study completion/discontinuation visit.

Haematology and Serum chemistry will be tested during post-surgical follow-up period (in RP+30 and RP+90) .

Serum PSA level and testosterone level will be analysed during post-surgical follow-up period, or at the study completion/discontinuation visit..

The visit will be terminated on,RP+90 days, the serum PSA level and testosterone as well as surgery associated complications will be collected.

Premature end of follow-up is needed as required by the patient or judged by investigator during follow-up, the ECOG performance status, hematology, serum chemistry, serum PSA, testosterone, concomitant medication and adverse drug reaction will be collected at the study completion/discontinuation visit.

If scheduled study assessments cannot be obtained because of a holiday, these assessments should be obtained at the soonest following date, unless the soonest following date is not more than 2 days away from the evaluation time of other planned studies.

5 STUDY ASSESSMENTS

The Electronic Data Capture (EDC) system will be used for data collection and query handling. The investigator will ensure that data are recorded on the eCRFs as specified in the study protocol and in accordance with the instructions provided.

The investigator ensures the accuracy, completeness and timeliness of the data recorded and of the provision of answers to data queries according to the Clinical Study Agreement (CSA) and Good Clinical Practice (GCP) requirements. The investigator will sign the completed eCRFs.

5.1 Efficacy assessments

5.1.1 Actual radical prostatectomy rate

Actual radical prostatectomy rate is defined as the rate of the subjects who perform radical prostatectomy after NHT

5.1.2 PSA test

Prostate-Specific Antigen (PSA) will be tested in local laboratory at each site.

PSA values at baseline and at each visit during the treatment and follow-up phase, up to and including the study treatment discontinued visit will be reported for each subject.

Post-surgical PSA decreased to less than 0.1 m/ml is defined as serum PSA < 0.1 m/ml during post-surgical follow-up period, or at termination visit

5.1.3 Tumor pathological features

Tumor pathological features will be evaluated in accordance with the postoperative pathology report issued by the department of Pathology at each study site.

Percentage of positive surgical margin of primary tumor is defined as the percentage of subjects with tumor at the margin resected in the postoperative pathological RP specimen.

Incidence of seminal vesicle invasion and involvement of pelvic lymph node is defined as the percentage of subjects with seminal vesicle invasion and those with unilateral or bilateral pelvic lymph node metastasis in the postoperative pathology.

Percentage of pathological down-stage is defined as the percentage of subjects with decreased pathological stage post operation than the preoperative clinical stage.

5.1.4 Surgical variables and complications

The main outcomes of interest are present in below to evaluate the local therapy (RP) of primary tumour. ^[22]

- Operative Duration is defined as the time (mins) from incision to finishing suturing.
- Intraoperative Estimated Blood Loss will be calculate using haematocrit parameters collected during the operation
- Duration of Indwelling Catheterization (Days) is defined as days from the start of surgery to removal of catheter. Institution/hospital local Urinary Catheter Indwelling and/or Removal Protocol will be applicable for each individual site.
- Complications. Percentage of subjects who experience complications and percentage of complication needing intervention in subjects who receive RP will be calculated.
- Urine function will be measured by dichotomous outcomes (continence or incontinence), where outcomes are defined as primarily the use of pads or absence of leakage. Time to Continence (Days) and urinary continence rate at 12 weeks after surgery will be reported.
- Erectile function will be measured by dichotomous outcomes (potent or impotent). Outcome results will be primarily determined by a single question will ask patients if they experience erections sufficiently firm for sexual intercourse. Potent rates in erectile function at 12 weeks after surgery will be calculated.

5.1.5 Exploratory endpoint

Occurrence of homologous recombination repair mutation (HRRm) will be explored in the patients with locally advanced prostate cancer in this study.

- All the subjects receiving surgical treatment will receive germline and tumor tissue gene test after surgery
- The gene test will be performed at the central laboratory in this study, the genes to be tested will include at least 15 homologous recombination repair related genes
- The 15 homologous recombination repair related genes include BRCA1, BRCA2, ATM, PALB2, CDK12, RAD54L, RAD51B, RAD51C, RAD51D, FANCL, CHEK1, CHEK2, PPP2R2A, BRIP1 and BARD1
- Percentage of subjects with harmful mutation of germline and tumor tissue HRR will be calculated respectively, and the rate of each harmful mutation will be recorded

5.2 Safety assessments

Table 1

5.2.1 Laboratory safety assessments

Blood and urine samples for determination of clinical chemistry, haematology, and urinalysis will be taken at the times indicated in the Study Plan (see Section 4).

Additional safety monitoring may be performed and investigator can suggest patients to take additional laboratory tests in the outpatient department if clinical indicated. The clinical chemistry, haematology and urinalysis will be performed at a local laboratory at the investigator site. Sample tubes and volume may vary depending on laboratory method used and routine practice at the site.

Table 1Laboratory Safety Variable	les		
Haematology/Haemostasis (whole blood)	Clinical Chemistry (serum or plasma)		
B-Haemoglobin (Hb)	S/P-Creatinine		
B-Leukocyte count	S/P-Bilirubin, total		
B-Leukocyte differential count (absolute count)	S/P-Alkaline phosphatase (ALP)		
B-Platelet count	S/P-Aspartate transaminase (AST)		
	S/P-Alanine transaminase (ALT)		
Urinalysis (dipstick)	S/P-Albumin		
U-Hb/Erythrocytes/Blood	S/P-Potassium		
U-Protein/Albumin	S/P-Calcium, total		
U-Glucose	S/P-Sodium		
	S/P-Creatine kinase (CK)		

The following laboratory variables will be measured:

The Investigator should make an assessment of the available results with regard to clinically relevant abnormalities. The laboratory results should be signed and dated and retained at centre as source data for laboratory variables.

5.2.2 Physical examination

A complete physical examination will be performed and include an assessment of the following: general appearance, skin, head and neck (including ears, eyes, nose and throat), lymph nodes, thyroid, respiratory, cardiovascular, abdomen, musculo-skeletal (including spine and extremities) and neurological systems.

A physical examination will be performed and include an assessment of the following: general appearance, respiratory, cardiovascular, abdomen.

5.2.3 ECG

Twelve-lead electrocardiograms (ECGs) are required to be performed as scheduled. ECGs will be reviewed by the investigator to determine if abnormality is clinically meaningful. For information on how AEs based on abnormality of ECGs should be recorded and reported, see Section 6.4.

5.2.4 Vital signs

Vital signs will include measurements of body temperature, heart rate, respiratory rate, systolic and diastolic blood pressure and be performed as scheduled.

5.2.4.1 Pulse and blood pressure

The subject should be seated for at least 5 minutes before the measurement of pulse, systolic and diastolic blood pressure.

5.2.4.2 Body temperature

There are various types of medical thermometers, as well as sites used for measurement of body temperature, including: in in the anus (rectum/rectal), in the mouth (oral temperature), under the arm (axillary temperature), in the ear (tympanic temperature). Those measurements of body temperature are acceptable.

5.2.5 Other safety assessments

Eastern Cooperative Oncology Group (ECOG) performance status scale will be used to evaluate the subject's general well-being and activities of daily life by investigator as schedule.

The following criterial are applied:

Grade 0: Fully active, able to carry on all pre-disease performance without restriction.

Grade 1: Restricted in physically strenuous activity but ambulatory and able to carry out work of a light or sedentary nature, e.g., light housework or office work

Grade 2: Ambulatory and capable of all self-care but unable to carry out any work activities. Up and about > 50% of waking hours

Grade 3: Capable of only limited self-care, confined to a bed or chair > 50% of waking hours

Grade 4: Completely disabled. Cannot carry on any self-care. Totally confined to bed or chair

Grade 5: Dead

6 SAFETY REPORTING AND MEDICAL MANAGEMENT

The PI is responsible for ensuring that all staff involved in the study are familiar with the contents of this section.

6.1 Definition of adverse events

An adverse event is the development of an undesirable medical condition or the deterioration of a pre-existing medical condition following or during exposure to a pharmaceutical product, whether or not considered causally related to the product. An undesirable medical condition can be symptoms (e.g., nausea, chest pain), signs (e.g., tachycardia, enlarged liver) or the abnormal results of an investigation (e.g., laboratory findings, electrocardiogram). In clinical studies, an AE can include an undesirable medical condition occurring at any time, including run-in or washout periods, even if no study treatment has been administered.

Radical prostatectomy is the expected endpoint in this study and does not belong to adverse event.

The term AE is used to include both serious and non-serious AEs.

6.2 Definitions of serious adverse event

A serious adverse event (SAE) is an AE occurring during any study phase (i.e., run-in, treatment, washout, follow-up), that fulfils one or more of the following criteria:

- Results in death
- Is immediately life-threatening
- Requires in-patient hospitalisation or prolongation of existing hospitalisation
- Results in persistent or significant disability/incapacity or substantial disruption of the ability to conduct normal life functions
- Is a congenital abnormality or birth defect
- Is an important medical event that may jeopardise the subject or may require medical intervention to prevent one of the outcomes listed above.

For further guidance on the definition of an SAE, see Appendix A to the Clinical Study Protocol.

Adverse Events (AEs) for malignant tumours reported during a study should generally be assessed as Serious AEs. If no other seriousness criteria apply, the 'Important Medical Event' criterion should be used. In certain situations, however, medical judgement on an individual

event basis should be applied to clarify that the malignant tumour event should be assessed and reported as a Non-Serious AE. For example, if the tumour is included as medical history and progression occurs during the study, but the progression does not change treatment and/or prognosis of the malignant tumour, the AE may not fulfill the attributes for being assessed as Serious, although reporting of the progression of the malignant tumour as an AE is valid and should occur. Also, some types of malignant tumours, which do not spread remotely after a routine treatment that does not require hospitalization, may be assessed as Non-Serious; examples include Stage 1 basal cell carcinoma and Stage 1A1 cervical cancer removed via cone biopsy.

The above instruction applies only when the malignant tumour event in question is a new malignant tumour (i.e., it is not the tumour for which entry into the study is a criterion and that is being treated by the IP under study and is not the development of new or progression of existing metastasis to the tumour under study). Malignant tumours that – as part of normal, if rare, progression – undergo transformation (e.g., Richter's transformation of B cell chronic lymphocytic leukemia into diffuse large B cell lymphoma) should not be considered a new malignant tumour.

6.3 Definitions of adverse drug reaction

An Adverse Drug Reaction (ADR) is an Adverse Event suspected to be causally related to the Investigational products.

An ADR is a response to a medicinal product which is noxious and unintended. Adverse reactions may arise from use of the product within or outside the terms of the marketing authorization or from occupational exposure

6.4 **Recording of adverse events**

6.4.1 Time period for collection of adverse events

Adverse Events will be actively collected and recorded from the time of informed consent up to 12 weeks after the last dose of Zoladex.

After the period, there is no obligation to actively report information on new AEs or SAEs occurring in study patients. If the investigator learns of any SAE, including a death, at any time after the period, he/she considers the event to be reasonably related to the study treatment or study participation, the investigator may notify AZ. Investigators will be encouraged to spontaneously report AZ products related AEs to AZ.

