4 STUDY PLAN AND TIMING OF PROCEDURES

4.1 Study schedule

Visit	1	2	3	4	5 ^e	6	7	8 ^g	For
Day	-28 to -1	1	85	169/E nd of treatm ent	EOT+30	RP+30	RP+90	Study completio n/disconti nuation	details see Protocol Section
Visit window	_	±5d	±5d	±5d		±5d	±5d	±5d	
Written informed consent	X								4.2
Demographics	X								4.2
Physical examination	X	Xa							4.2
Medical/surgical history	X								4.2
Inclusion/exclusion criteria	X								4.2
ECOG performance status	X	Xa	X	X	Xª		X	X	4.2, 4.3 & 4.4
Vital signs, body weight	X	Xa	X	X	Xª		X	X	4.2
ECG	X	Xa			Xa				4.2
Imaging (CT or MRI)	x					X (clinical ly indicated)	X (clinical ly indicated)	X (clinical ly indicated)	4.2, 4.3 & 4.4
Bone scan	X								4.2, 4.3 & 4.4
Gleason score	X				X				4.2 & 4.4
Zoladex and Casodex treatment		Xc	Xc						4.3
RP evaluation				X					4.3
RP					X				4.4
Assessment after radical prostatectomy plus ePLND					X				4.4
ADT after RP						X ^b	Xb	X ^b	4.4

Visit	1	2	3	4	5°	6	7	8 ^g	For
Day	-28 to -1	1	85	169/E nd of treatm ent	EOT+30	RP+30	RP+90	Study completio n/disconti nuation	details see Protocol Section
Visit window	-	±5d	±5d	±5d		±5d	±5d	±5d	
Concomitant medication	X	X	X	X	X	X	X	X	4.2, 4.3 & 4.4
Adverse event	X	X	X	X	X ^d	X ^d	X ^d	X ^d	4.3 & 4.4
Haematology and clinical chemistry	X	Xa	X	X		X	X	X	4.2, 4.3 & 4.4
Blood germline forHRRm collected				X(all patien ts)					4.3
Tumor tissue for HRRm collected					X ^h				4.4
Urinalysis	X	Xa							4.2
Serum testosterone level	X	Xa	X	X		X	X	X	4.2, 4.3 & 4.4
Serum PSA level	X	Xa	X	X		X	X	X	4.2, 4.3 & 4.4

a. If assessed within 7 days before enrolment and meets the stated eligibility criteria (if applicable), it does not need to be repeated on Day 1 of study treatment unless investigator believes that it is likely to have changed significantly.

b. The treatment will be based on investigator's discretion

c. Casodex will be administrated till Week 24

d. AEs will be actively collected from ICF to 12 weeks after last dose of Zoladex

e. Radical prostatectomy should be performed within 30 days after end of NHT. The visit will be ended for the patients without radical operation following NHT after collection of the reason for failure to receive an operation.

f. The visit will be completed after follow-up for three months following radical operation

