6.4.9 Deaths

All deaths that occur during the study must be reported as follows:

• Death clearly the result of disease progression should be reported to the study monitor at the next monitoring visit and should be documented in the eCRF but should not be reported as an SAE.

• Where death is not due (or not clearly due) to progression of the disease under study, the AE causing the death must be reported to the study monitor as a SAE within 24 hours. The report should contain a comment regarding the co involvement of progression of disease, if appropriate, and should assign main and contributory causes of death.

• Deaths with an unknown cause should always be reported as a SAE. A post mortem maybe helpful in the assessment of the cause of death, and if performed a copy of the post-mortem results should be forwarded to AstraZeneca within the usual timeframes .

6.5 **Reporting of serious adverse events**

All SAEs from the time of informed consent up to 12weeks after the last dose of Zoladex have to be reported, whether or not considered causally related to the IP, or to the study procedure(s). All SAEs will be recorded in the CRF.

If any SAE occurs in the course of the study, then Investigators or other site personnel inform the appropriate AstraZeneca representatives within one day i.e., immediately but **no later than 24 hours** of when he or she becomes aware of it.

The designated AstraZeneca representative works with the Investigator to ensure that all the necessary information is provided to the AstraZeneca Patient Safety data entry site within 1 calendar day of initial receipt for fatal and life threatening events and within 5 calendar days of initial receipt for all other SAEs. In addition, the investigator should report the SAE to China Authority according to local regulation and Local Ethics Committee (EC) according to local requirement.

For fatal or life-threatening AEs where important or relevant information is missing, active follow-up is undertaken immediately. Investigators or other site personnel inform AstraZeneca representatives of any follow-up information on a previously reported SAE within one calendar day i.e., immediately but **no later than 24 hours** of when he or she becomes aware of it.

Once the Investigators or other site personnel indicate an AE is serious in the EDC system, an automated email alert is sent to the designated AstraZeneca representative.

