7.2 Dose and treatment regimens

Zoladex[®] 10.8 mg implant will be administered subcutaneously every 12 weeks for 24 weeks.

Casodex[®] in combination with Zoladex[®] is one 50 mg tablet once daily (morning or evening), with or without food. It is recommended that Casodex[®] be taken at the same time each day. Treatment with Casodex[®] should be started at the same time as treatment with Zoladex[®] and continued for 24 weeks.

Treatment after RP will be dependent on the investigator's discretion.

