4.3.7.4 Adverse events(AEs)

Treatment-emergent AEs (TEAEs) are defined as the AEs occurring on or after the first dosing of study drug and up to 4 weeks after discontinuation of study drug. All AEs will be listed and summarized. See Appendix 1 for handling of partial dates for AEs, in the case where it is not possible to define TEAEs, the AEs will be identified as TEAEs.

AEs will be categorized into one or more of the following categories depending on the type of events reported:

- AEs
- SAEs
- Treatment-emergent AEs,
- Drug-related AEs (Zoladex related, Casodex related)
- Drug-related SAEs
- AEs leading to study drug discontinuation
- AEs with an outcome of death
- AEs of CTCAE Grade 3 or higher

An overall summary of the number and percentage of subjects in each category will be presented, as will an overall summary of the number of events in each category.

The number and percentage of subjects with TEAEs in each category above will be summarized and events in each category will be further summarized by MedDRA SOC and PT.

All related information (such as SOC/PT, CTCAE Grade, outcome, etc.) about adverse event will be listed for each subject and each term, based on following category: Deaths, SAEs and AEs. Above analyses will be performed based on FAS.

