7. APPENDIX 1: PARTIAL DATE CONVENTIONS

Imputed dates will NOT be presented in the listings.

Algorithm for Treatment-emergent Adverse Events:

START DATE	STOP DATE	ACTION
Known	Known/Partial/Missing	If start date < study treatment start date, then not TEAE
		If start date >= study treatment start date, then TEAE
Partial, but known	Known/Partial/Missing	Not TEAE
components show that it cannot be on or after study treatment start date	, , , , , , , , , , , , , , , , , , , ,	
Partial, could be on or after study treatment start date	Known/ Partial/Missing	Impute stop date as latest possible date (i.e. last day of month if day unknown or 31st December if day and month are unknown), if partial or missing date exist.
		If stop date < study treatment start date, then not TEAE
		If stop date >= study treatment start date, then TEAE
Missing	Known/ Partial	Impute stop date as latest possible date (i.e. last day of month if day unknown or 31st December if day and month are unknown), if partial or missing date exist.
		If stop date < study treatment start date, then not TEAE
		If stop date >= study treatment start date, then TEAE
	Missing	Assumed TEAE

Algorithm for Prior / Concomitant Medications:

START DATE	STOP DATE	ACTION
Known	Known	If stop date < study treatment start date, assign as prior If stop date >= study treatment start date and start date <= end of treatment+3 months, assign as concomitant If start date > end of treatment+3 months, assign as post study
	Partial	Impute stop date as latest possible date (i.e. last day of month if day unknown or 31st December if day and month are unknown), then: If stop date < study treatment start date, assign as prior
		If stop date >= study treatment start date and start date <= end of treatment+3 months, assign as concomitant If start date > end of treatment+3 months, assign as post treatment
	Missing	If start date > end of treatment+3 months, assign as post treatment If start date > end of treatment+3 months, assign as post treatment If start date > end of treatment+3 months, assign as post treatment
Partial	Known	Impute start date as earliest possible date (i.e. first day of month if day unknown or 1st January if day and month are unknown), then: If stop date < study treatment start date, assign as prior If stop date >= study treatment start date and start date <= end of treatment+3 months, assign as concomitant If start date > end of treatment+3 months, assign as post treatment

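### On the nominal schedule AE/SAE collection ends on Day 169 as the surgery window opens, other protocol sections contradict that cut-off, and the 4-week TEAE limit matches neither the collection period nor SAP Appendix 1

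*Protocol*

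**What the plan says.** **Collection period.** Protocol 6.4.1 sets it: "Adverse Events will be actively collected and recorded from the time of informed consent up to 12 weeks after the last dose of Zoladex". Footnote d to the schedule (4.1), attached to the AE marks at V5 to V8, repeats it: "AEs will be actively collected from ICF to 12 weeks after last dose of Zoladex". Protocol 6.5 opens with the same limit for SAEs: "All SAEs from the time of informed consent up to 12weeks after the last dose of Zoladex have to be reported". Section 6.6 applies it to adverse drug reactions. Once the period is over, 6.4.1 states that "there is no obligation to actively report information on new AEs or SAEs occurring in study patients". Even for an SAE judged related to treatment or participation, notifying the sponsor is then optional.

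**Text pointing the other way.**
- Protocol 4.4 lists adverse events among the items collected at V5 (EOT+30).
- The schedule marks AEs at V5, V6, V7 and V8.
- Protocol 6.2 defines an SAE as arising in any study phase and names follow-up among them.
- A later paragraph of 6.5 asks for notice within 24 hours of any SAE while the study is running.
- Protocol 6.4.9 requires all deaths during the study to be reported, with no 12-week limit.

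**Treatment-emergent events.** Protocol 8.5.2 and SAP 4.3.7.4 define TEAEs as AEs "occurring on or after the first dosing of study drug and up to 4 weeks after discontinuation of study drug". SAP Appendix 1, in the row for a fully known start date, says only: "If start date >= study treatment start date, then TEAE".

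**The concern.** The trial gives 24 weeks of hormone therapy in order to make surgery possible, and both safety and surgical complications are secondary objectives. If the collection period closes as the surgery window opens, the period of highest procedural risk depends on which sentence a site follows. A site working from 6.4.1 and footnote d may stop recording AEs and SAEs at the end-of-treatment visit. A site working from 4.4 and the later part of 6.5 will carry on. With about 15 sites, the perioperative SAE data could differ by site for reasons unrelated to the patients.

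Surgical complications are captured separately up to RP+90, but no section gives those records a seriousness assessment, a CTCAE grade, a causality rating or a 24-hour route to the sponsor. A non-surgical event after Day 169 has no clear place at all.

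The TEAE problem is separate. Two programmers, one following SAP 4.3.7.4 and one following Appendix 1, could produce different TEAE tables from the same data.

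**Working it through.** **Inputs**
- Zoladex: "10.8 mg implant will be administered subcutaneously every 12 weeks for 24 weeks" (Protocol 7.2), given at V2 (Day 1) and V3 (Day 85) in the schedule.
- Casodex: to Week 24, so the last dose is on Day 168 (footnote c).
- End of treatment (EOT): Day 169. RP: within 30 days after it (4.4).
- Visit window: ±5 days. Early termination is considered only when an implant is delayed by more than 7 days (3.6).
- Collection limit: 12 weeks = 84 days after the last implant.
- TEAE limit: 4 weeks = 28 days after discontinuation of study drug.

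**Step 1. End of collection, nominal schedule.** 85 + 84 = Day 169. This equals the protocol's own EOT day.

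**Step 2. Surgery and follow-up.** RP falls between Day 169 and 169 + 30 = Day 199. RP+90 falls between 169 + 90 = Day 259 and 199 + 90 = Day 289. The time after collection closes is therefore 259 − 169 = 90 to 289 − 169 = 120 days.

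**Step 3. Effect of windows and delays**

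| Second implant | Collection ends |
|---|---|
| Day 80 (−5) | Day 164 |
| Day 85 | Day 169 |
| Day 90 (+5) | Day 174 |
| Day 92 (7-day delay) | Day 176 |

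An early RP can therefore fall a few days inside the period. Even with collection open to Day 176 and RP on Day 169, 259 − 176 = 83 days of follow-up lie outside. A subject with one implant has collection to 1 + 84 = Day 85, and an RP after an early stop could fall before that.

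**Step 4. End of the TEAE window for a completer.** The documents do not say how to date discontinuation for a two-drug regimen.

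| Counted from | TEAE window ends | Against Day 169 |
|---|---|---|
| Last implant | 85 + 28 = Day 113 | 56 days earlier |
| Last Casodex dose | 168 + 28 = Day 196 | 27 days later |
| EOT visit | 169 + 28 = Day 197 | 28 days later |
| Appendix 1 | no end date | open-ended |

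No reading coincides with the collection period.

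**Step 5. Early stopper (illustration).** A subject has one implant and stops both drugs on Day 30. The TEAE window in 4.3.7.4, counted from Day 30, ends on 30 + 28 = Day 58. Collection runs to Day 85. Events starting in the remaining 85 − 58 = 27 days are TEAEs under Appendix 1 but not under 4.3.7.4.

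**The case against.** A reader might infer that collection always stops before any prostatectomy, so that perioperative SAEs simply need not be reported. The documents do not support that. Visit windows, a tolerated implant delay or an early stop can place an RP inside the period, and the RP analysis set expressly admits subjects who stopped treatment early. Sections 4.4, 6.2, 6.4.9 and the later part of 6.5 all require or presuppose reporting beyond the cut-off. The protocol contradicts itself; it does not leave a clean gap.

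It can also be said that operative harm has its own data stream. Complications are a separate secondary objective, are collected to RP+90, coded in MedDRA, tabulated by SOC and PT, and listed with dates and outcome. The AE objective concerns the hormone therapy, so a window matching the 12-week implant interval is coherent. This stands as a defence of the efficacy and complication tables. It does not supply an SAE route for complications, and it does not settle which sentence sites should follow.

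On TEAEs, the objection has some force. If nothing is recorded after Day 169, a limit at Day 196 or 197 and no limit at all give the same counts for completers. The two rules then differ for early stoppers, for completers if the window is counted from the last implant (Day 113), and for any later AE recorded under 4.4 or the V5 to V8 marks. Saying that 27 of the 28 post-treatment TEAE days hold no data is true on one reading only. Nor are the excluded events lost: SAP 4.3.7.4 also lists and summarises all AEs.

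Appendix 1 could be read as a partial-date convention only. But the row at issue covers start dates that are fully known.

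**Conclusion.** The point holds as an inconsistency to be reconciled. On the nominal schedule the stated AE, SAE and ADR collection period ends on Day 169 as the surgery window opens (Day 164 to 176 with windows or a 7-day delay). That leaves a nominal 90 to 120 days to RP+90 governed by conflicting instructions. The 4-week TEAE limit differs from the end of collection by −56, +27 or +28 days, depending on an undefined date, and Appendix 1 has no limit.

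This rests on three assumptions: the last Zoladex dose means the last study implant and not commercially supplied therapy after RP; the nominal visit days apply unless stated; and the footnote on the V5 to V8 AE marks means what it says.

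It should be fixed, but it is not critical to the main result. The primary endpoint is unaffected and complications are analysed separately. What is at risk is the consistency of perioperative SAE reporting and the reproducibility of the TEAE tables.

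**What to change.** **Protocol.** Reconcile 6.4.1, 6.5, 6.6 and footnote d with 4.4, 6.2, 6.4.9 and the V5 to V8 AE marks by stating one end date for AE and SAE collection.
- Operated subjects: to RP+90.
- Unoperated completers: to the existing V5 contact at EOT+30 (nominally Day 199). SAP 4.1, which makes their last visit the EOT visit, needs to match.
- Unoperated early stoppers: at least to the TEAE end date below.
- State that a surgical complication meeting an SAE criterion goes through the SAE process.

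**SAP.** Define the TEAE end date for the two-drug regimen so that it lies within the collection period and is no earlier than 12 weeks after the last implant. One definition that works is the later of 12 weeks after the last implant and 4 weeks after the last Casodex dose. That gives Day 196 for a nominal completer and Day 85 for the Day-30 stopper. Use the same upper limit in 4.3.7.4 and Appendix 1, align Protocol 8.5.2, and tabulate events from RP onward separately.

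**Cost.** Wording changes in both documents and more AE entry. The visits for operated subjects and unoperated completers are already scheduled and carry AE marks.
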